4.2.2.1 Seizure Control

To assess seizure control during the 12-week treatment period, the subset of ITT patients who achieve $\geq 50\%$ reduction in 28-day primary type seizure frequency during the 12-week treatment period compared to baseline will be summarized as was described for the primary efficacy analysis. The calculation of percent reduction from baseline in seizure frequency is described in Section 3.1.3.6.

Percent change values meeting criteria of interest, i.e. $\geq 25\%$ reduction, $\geq 50\%$ reduction and $\geq 75\%$ reduction from baseline will be flagged in the by-patient listing of seizure data.

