9.6. Efficacy Analyses

Since this is an OL proof of concept study, no inferential statistical testing will be conducted. All efficacy outcomes will be assessed descriptively with point estimates and 95% confidence intervals.

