9.6.2.1. Secondary Efficacy: Seizure control

- Percentage of patients experiencing a $\geq 50\%$ reduction in 28-day primary seizure frequency through the end of the 12-week treatment period compared to the 4-week Baseline Period

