1.2.2.1 Secondary Efficacy Endpoint – Seizure Control

- Percentage of patients experiencing a $\geq 50\%$ reduction in 28-day primary seizure frequency through the end of the 12-week treatment period compared to the 4-week baseline period.

Derived seizure secondary efficacy endpoints will be based on data through the end of the 12-week treatment period relative to the 4-week baseline period as defined in [Section 3.1.3](#).

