4.2 EFFICACY ANALYSES

4.2.1 Primary Efficacy Analysis

4.2.1.1 Primary Analysis

The primary efficacy endpoints, the percent change in 28-day primary seizure type frequency through the end of the 12-week treatment period (Part A; 4-week titration and 8-week maintenance) relative to the baseline, is defined in Section 1.2.1. The calculation of the primary endpoint is described in Section 3.1.3.

Descriptive summaries including the number of patients with non-missing primary seizure data, mean arithmetic change and percent change in 28-day primary seizure type frequency from baseline and associated 95% confidence intervals, SD, minimum, median and maximum values will be presented for the baseline period, 4-week titration period, 8-week maintenance period and 12-week treatment period. All patients in the ITT population and all available seizure data within Part A of the study will be included in these analyses regardless of whether the patient stopped taking IP or took rescue medication.

Additionally, a by-patient listing of seizure data collected during Part A will be provided.

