4.2.2 Secondary Efficacy Analysis

Secondary efficacy endpoints are defined in Section 1.2.2. Analyses of secondary

efficacy endpoints will be based on the ITT population.

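### SAP 4.2.2.1 summarises change among responders instead of the responder percentage: the endpoint gets no 95% CI, and the derivation reference is wrong

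*SAP*

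**What the plan says.** SAP 1.2.2.1 and protocol 9.6.2.1 list a single seizure-control secondary endpoint. It is the percentage of patients reaching at least a 50% "reduction in 28-day primary seizure frequency through the end of the 12-week treatment period compared to the 4-week baseline period".

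SAP 4.2.2 points back to that definition ("Secondary efficacy endpoints are defined in Section 1.2.2") and sets the ITT population. SAP 4.2.2.1 then gives the analysis. It takes the ITT patients who reached the threshold and states that this subset "during the 12-week treatment period compared to baseline will be summarized as was described for the primary efficacy analysis". It adds that values passing 25%, 50% and 75% will be flagged in a listing.

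The primary analysis in SAP 4.2.1.1 is continuous. It reports n, "mean arithmetic change and percent change in 28-day primary seizure type frequency from baseline and associated 95% confidence intervals", SD, minimum, median and maximum, and these "will be presented for the baseline period, 4-week titration period, 8-week maintenance period and 12-week treatment period".

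For the derivation, SAP 4.2.2.1 says: "The calculation of percent reduction from baseline in seizure frequency is described in Section 3.1.3.6".

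Protocol 9.6 says: "All efficacy outcomes will be assessed descriptively with point estimates and 95% confidence intervals".

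**The concern.** The endpoint asks how many patients responded. The analysis section, read as written, describes how much the responders improved. These are different quantities, and the second cannot stand in for the first: adding or removing non-responders changes the response rate but leaves every entry of the responder summary unchanged.

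The interval is the main loss. A 95% CI around mean change among responders does not say how uncertain the response rate is, and with about 30 patients that uncertainty is large. The study is single-arm with no testing, so the point estimate and its interval are all this endpoint can deliver.

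**Working it through.** **Does the specified method produce the endpoint?**

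| Item | Endpoint (SAP 1.2.2.1, protocol 9.6.2.1) | Analysis (SAP 4.2.2.1 via 4.2.1.1) |
|---|---|---|
| Patients | all patients | responders only |
| Quantity | percentage of patients | mean and distribution of change |
| 95% CI | none stated in the SAP | for mean change |
| Time frame | 12 weeks | baseline, titration, maintenance, 12 weeks |

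The percentage can be recovered. SAP 2.1 prescribes counts and percentages for categorical variables, 4.1.1 reports the size of each analysis set, and the responder summary carries its own n. None of these sections supplies a confidence interval for a proportion. By comparison, SAP 4.2.2.2 writes out number and percentage for the CGI scales.

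**What the responder summary can show.** In the 12-week row every value is at or below −50% by selection. The titration and maintenance rows are not bounded in this way. Take an illustrative patient with a complete diary (28 titration days, 56 maintenance days), 20 seizures per 28 days at baseline, 16 seizures in titration and 14 in maintenance:

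- Titration: (16 − 20)/20 = −20%.
- Maintenance: 14/56 × 28 = 7, so (7 − 20)/20 = −65%.
- 12 weeks: (16 + 14)/84 × 28 = 10, so (10 − 20)/20 = −50%.
- Check: (4 × −20 + 8 × −65)/12 = −50%.

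This patient is a responder whose titration value is well above −50%.

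**Size of the missing interval.** N = 30 is the planned number treated (SAP 1.3.2). The documents give no expected response rate, so the counts k below are assumptions. The exact (Clopper-Pearson) limits are

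- lower = Beta quantile at 0.025 with parameters (k, N − k + 1), or 0 when k = 0;
- upper = Beta quantile at 0.975 with parameters (k + 1, N − k).

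| k/30 | Percentage | Exact 95% CI | Width (points) |
|---|---|---|---|
| 0 | 0% | 0–11.6 | 11.6 |
| 1 | 3.3% | 0.1–17.2 | 17.1 |
| 5 | 16.7% | 5.6–34.7 | 29.1 |
| 10 | 33.3% | 17.3–52.8 | 35.5 |
| 15 | 50.0% | 31.3–68.7 | 37.4 |

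With 0 or 1 responder there is no SD, so the interval for the responder mean cannot be computed. The interval for the proportion still can.

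**The cross-reference.** SAP 3.1.3.6 defines percent change in seizure-free days, where improvement is an increase. Percent change in 28-day seizure frequency is in 3.1.3.3. Because the citing sentence names seizure frequency, a programmer would probably see the slip. It is a numbering error only.

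**The case against.** The strongest reply is that little is lost. The percentage is inferable, the ITT population is set, and once n and N are reported any reader can compute a binomial interval. No test, sample-size claim or multiplicity rule depends on it. The reference to the primary analysis could also be read as importing only its population, data rules and CI convention into an endpoint already defined as a percentage. The table templates might settle that, but SAP section 8 places them in a separate document that was not supplied.

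There is also a version gap. The sentence requiring intervals is in the protocol dated 11 Jun 2021, while the SAP cites the version of 12 May 2020. Whether that version contained the sentence cannot be checked. The current synopsis says only that efficacy analyses are descriptive. Read strictly, protocol 9.6 would require intervals for the CGI endpoints too, and SAP 4.2.2.2 gives none.

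Most of this stands as qualification and limits the severity. It does not remove the point. The mismatch between the SAP's endpoint and its analysis, and the wrong section number, are internal to the SAP and do not depend on the protocol version. A descriptive analysis can carry intervals, and protocol 9.6 pairs the two. The looser reading is possible, but it is not what the section says: the section names a subset of patients and refers to a continuous summary. A named secondary endpoint should not depend on inference or on templates held elsewhere.

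**Conclusion.** The concern holds and should be fixed. SAP 4.2.2.1 specifies a summary of the wrong quantity for the only seizure-control secondary endpoint. Its one confidence interval is for mean change in a group selected to be at or below −50% over 12 weeks, no SAP text gives an interval for the responder percentage, and the derivation reference is wrong.

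At N = 30, and for assumed counts of 5 to 15 responders, the unreported exact interval is about 29 to 37 percentage points wide. The effect is on reporting and precision only. No error rate is affected, and the point estimate can be recovered from other SAP text. The mismatch and the section number rest on the SAP alone. The requirement for an interval rests on the current protocol text.

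**What to change.** Add one sentence to SAP 4.2.2.1, for example: *For the ITT population, the count and percentage (n/N) of patients whose 28-day primary seizure frequency over the 12 weeks of Part A treatment is at least 50% below baseline will be reported, with an exact (Clopper-Pearson) 95% CI.*

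A Wilson interval would also serve; what matters is that one method is named in advance. It would help to state in the same place how N treats an ITT patient with no post-baseline diary data, since SAP 2.2 admits patients on any post-baseline efficacy assessment.

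Keep the by-period summary among responders as supplementary. Change the reference from Section 3.1.3.6 to Section 3.1.3.3.

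The cost is a sentence or two of SAP text and one section number. No planned summary is removed, and no data collection or design change is needed.

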4.2.2.2 CGI-I and CGI-C

The CGI-C in target behavior includes two 7-point Likert items which the parent or caregiver uses to rate the severity of the target behavior at baseline and to assess change in the target behavior after initiation of IP relative to baseline. The severity scale ranges from 1 = normal to 7 = very severe problem, and the change scale ranges from 1 = very much improved to 7 = very much worse.

The target behavior chosen and the baseline severity of this behavior will be summarized. For post-baseline visits, change in this severity since the start of the study will be summarized. The number and percentage of ITT patients receiving each CGI-C change rating will be summarized by visit.

The CGI-I contains two 7-point Likert scales for baseline overall severity of the patient's presentation (ranging from 1 = normal to 7 = very severe problem) and overall global impression of change relative to baseline (ranging from 1 = very much improved to 7 = very much worse). The number and percentage of patients receiving each CGI-C rating will be summarized. The CGI-I responses from the clinician and from the parent/caregiver will be presented separately by visit.

A listing of CGI-C and CGI-I data collected by visit for each patient will be provided.

4.3 SAFETY ANALYSIS

Safety analyses will be based on all patients in the Safety population, unless otherwise indicated. Data will be summarized for Part A, Part B and across the entire study for those patients participating in both parts.

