4.1.1. Inclusion Criterion (Part B)

1. Patients have experienced \geq 35% reduction in primary seizure frequency during the Part A treatment period compared to the 4-week Baseline Period.

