9.7. Safety Analyses

Safety will be reported for all patients. The results in Part A and Part B will be summarized separately and then the combined results in Part A and Part B will be summarized together. Adverse events will be tabulated by overall, system organ class, and Preferred Term using the Medical Dictionary for Regulatory Activities (MedDRA) coding system. Incidence and percentage of AEs will be presented. Additional tables, with AEs classified by severity and by only those related to drug as assessed by the investigator will be presented. Subset listings will be produced for AEs that cause withdrawal and for SAEs. Clinical laboratory tests (hematology, chemistry and urinalysis), vital signs (temperature, BP, pulse rate), weight, and ECGs will be summarized using descriptive statistics including changes from baseline. Change in C-SSRS scores where applicable will be determined. Physical, neurological and developmental examinations will be summarized using number and percentage of patients with abnormalities.

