4.3.1 Extent of Exposure

Exposure to study medication (GNX) will be summarized as the number of days on treatment, percentage of days dosed, maximum daily dose received, and total dosage received. The denominator for the percentage of days of study drug is the number of days the patient is on treatment in the respective part of the study. If the patient stops taking IP during the study, the last day that drug was taken will be used as the last day of treatment. For patients who are ongoing at the end of a specific part of the study, the last known

treatment date will be used for the last day on treatment. Exposure data will be summarized for Parts A and B of the study separately as well as overall exposure for all patients.

A listing of exposure data for each patient including total daily dose, start and end dates, and reason for any dose change will also be provided.

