4.3.2 Adverse Events

Adverse events (AEs) are collected from the time of informed consent/assent through the defined follow-up period. AEs are coded using MedDRA dictionary, version 22.0 and are categorized by system organ class (SOC) and preferred term (PT). A treatment-emergent AE (TEAE) is defined as an AE that starts or worsens on or after the first day of dosing with IP. Analyses of TEAEs for Part A of the study will include AEs that start or worsen during Part A and will not include any AE that starts or worsens during Part B. For Part B of the study, TEAEs will be include events that start or worsen after the first day of Part B relative to the first day of Part B. TEAEs over the entire study will be summarized for patients who participate in both Parts A and B of the study.

Tabulations of AEs will be by patient such that an individual is only counted once per summary category. Detailed by-patient listings of all AEs reported during the study will be provided and will include verbatim and coded terms for each AE.

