4.3.2.1 Overview of Adverse Events

A summary of AEs reported during the study will be presented. The number and percentage of patients in the Safety Population who reported at least one occurrence of an event in one of the following categories will be summarized:

- Any TEAE
- TEAE with causality related to study drug
- Any SAE
- TEAE leading to discontinuation of study drug
- TEAEs by worst severity
- TEAEs with an outcome of death

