4.3.2.2 Incidence of TEAEs

The number and percentage of patients reporting at least one TEAE during Part A, Part B and overall will be summarized by MedDRA System Organ Class (SOC) and preferred term (PT). The summary will be sorted by descending frequency within SOC and PT within SOC.

A detailed listing of AEs for each patient will be provided. The listing will include the

verbatim term reported by the Investigator, MedDRA SOC and PT, onset date/time, end date/time, severity, seriousness (yes/no), seriousness reason, relationship to study drug, action taken, withdrawal from study, treatment required, and outcome.

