4.3.4 Vital Signs and Physical, Neurological and Developmental Examination Findings

4.3.4.1 Vital Signs

Vital signs measured in this study include systolic and diastolic blood pressure, heart rate, respiratory rate, and body temperature. Baseline for vital signs will be the values obtained at the last assessment prior to the first dose of IP, typically Visit 2, Day 0. Change from baseline is calculated as the post-baseline value minus the baseline value. Missing values will not be imputed.

Absolute values and changes from baseline in vital signs at each visit will be summarized for Parts A and B and overall in the Safety Population using descriptive statistics (n, mean, SD, median, minimum, and maximum). A by-patient, by-visit listing of vital signs collected and height and weight recorded will be provided.

All vital signs included the parameter values and overall interpretations will be listed. Changes from baseline physical examination findings will also be listed individually by patient.

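### The SAP limits whole-study safety summaries to patients who entered both parts, against protocol 9.7 and the SAP's own Safety Population tables

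*SAP*

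**What the plan says.** Protocol 9.7 states: "Safety will be reported for all patients. The results in Part A and Part B will be summarized separately and then the combined results" of the two parts are to be presented together. It does not require entry into Part B. The synopsis says the same.

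SAP 2.2 defines the Safety population by a single dose of ganaxolone. SAP 4.3 makes that population the default for safety, subject to exceptions, and the next sentence gives one: "Data will be summarized for Part A, Part B and across the entire study for those patients participating in both parts". SAP 4.3.2 repeats it for adverse events: "TEAEs over the entire study will be summarized for patients who participate in both Parts A and B of the study".

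Other overall outputs in the SAP carry no such limit:

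- Exposure (4.3.1) is given for Parts A and B "separately as well as overall exposure for all patients".
- The adverse event overview (4.3.2.1) counts "The number and percentage of patients in the Safety Population who reported at least one occurrence of an event" in each listed category.
- Vital signs (4.3.4.1) "will be summarized for Parts A and B and overall in the Safety Population".

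The main incidence table by organ class and term (4.3.2.2) has an overall summary but names no population: "The number and percentage of patients reporting at least one TEAE during Part A, Part B and overall will be summarized by MedDRA". The severity, relationship and SAE tables (4.3.2.3 to 4.3.2.5) name none either.

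**The concern.** Patients who enter Part B are not a neutral sample of those treated. Protocol 4.1.1 requires at least a 35% "reduction in primary seizure frequency during the Part A treatment period compared to the 4-week Baseline Period", with exceptions by sponsor approval. Protocol 4.2.1 excludes anyone who has developed a condition that makes ganaxolone unsafe. A both-parts table therefore leaves out, from numerator and denominator alike, patients who stopped during Part A and completers who did not go on.

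Two things are at stake. The combined summary in protocol 9.7 would describe continuers only. And two overall adverse event outputs in one report could rest on different denominators, all treated patients in the overview and continuers in the table by organ class and term, so their counts of patients with any TEAE need not agree.

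A smaller point concerns the day on which Part A ends for TEAEs. SAP 4.3.2 counts Part B events only after that part's first day. The concomitant-medication rule in 4.1.5 gives the first extension dosing day to Part B. The efficacy windows in 3.2 start the extension the day after Visit 5.

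**Working it through.** The plan states no figure to reproduce, so the check is a comparison of the text followed by an illustration of size.

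**Which population governs.** The 4.3 default yields where the SAP indicates otherwise, and the sentence after it does so for the entire study. For TEAEs, 4.3.2 is the more specific rule. The overview, exposure and vital-sign sections override it by naming their own population. Section 4.3.2.2 does not, so the both-parts rule governs its overall summary most directly. The same holds for any whole-study version of 4.3.2.3 and 4.3.2.4. The SAE table in 4.3.2.5 is not confined to TEAEs, so only the general sentence in 4.3 reaches it.

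**Size.** Let N be the number treated, nB those who enter Part B, nA = N − nB, and rB and rA the event rates in the two groups.

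- All treated: (nB × rB + nA × rA) / N
- Both parts: rB
- All treated minus both parts: (nA / N) × (rA − rB)

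N = 30 is the plan in SAP 1.3.2. The documents give no continuation rate, so nB = 16, 20 and 24 are assumed, as is a 20-point difference in rates.

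| nB | nA | nA / N | Shift for a 20-point difference |
|---|---|---|---|
| 16 | 14 | 46.7% | 9.3 points |
| 20 | 10 | 33.3% | 6.7 points |
| 24 | 6 | 20.0% | 4.0 points |

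Examples with assumed event counts:

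| Continuers | Part A only | All treated | Both parts |
|---|---|---|---|
| 5/16 | 9/14 | 14/30 = 46.7% | 31.3% |
| 8/20 | 6/10 | 14/30 = 46.7% | 40.0% |
| 8/16 | 7/14 | 15/30 = 50.0% | 50.0% |
| 3/16 | 1/14 | 4/30 = 13.3% | 18.8% |

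The both-parts rate can be lower, equal or higher. Continuers contribute Part A events too and are followed for longer.

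Discontinuations in Part A because of an adverse event would be understated if the filter reached them: 0/16 against 4/30 (13.3%), or 0/24 against 2/30 (6.7%), again with assumed counts. Section 4.3.2.1 counts discontinuations of study drug due to TEAEs in the Safety Population, so this arises only if the rule were applied against that section.

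**Boundary day.** If the first extension day belongs to Part B, an event starting that day is too early for the Part B table and is barred from the Part A table. It would still appear in the whole-study table and the listings. If the day belongs to Part A, there is no gap.

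**The case against.** The protocol's promise to report safety for all patients can be called met, because Part A tables, the overview and the listings cover everyone treated, and its clause on combined results states no denominator. The SAP was also written to protocol Version 2 of 12 May 2020, while the protocol supplied is dated 11 June 2021, and the earlier text cannot be seen. On this view the problem shrinks to one ambiguous overall column in 4.3.2.2. The study is single-arm and descriptive, the primary safety objective ends at Week 12 where nobody is dropped, and a both-parts table is a reasonable output for the long-term objective.

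Part of this stands. No event disappears from the report, the direction of the distortion is not fixed, and a both-parts table is legitimate as an extra. The version gap is real, but the conflict inside the SAP does not depend on it, and SAP section 6 declares no change to planned analyses. Reading the protocol's combined clause as limited to continuers needs a filter that its paragraph does not contain. The ambiguity in 4.3.2.2 is itself the fault: two programmers could build different tables from the same plan.

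**Conclusion.** The concern holds. SAP 4.3 and 4.3.2 restrict the whole-study summaries in a way that conflicts with protocol 9.7 and with SAP 4.3.1, 4.3.2.1 and 4.3.4.1. If 16 to 24 of 30 treated patients continue, 14 to 6 of them leave the overall TEAE table, and each 20 points of difference in event rate between the groups moves the result by 9.3 to 4.0 points. The 30 is planned; the continuation numbers and event rates are assumptions. The sign cannot be predicted.

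This should be corrected, but it does not undermine the safety assessment, because the Part A tables that serve the primary objective keep every treated patient. The boundary-day point is minor and conditional on which part owns that day.

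**What to change.** In SAP 4.3 and 4.3.2, base every whole-study safety summary on the Safety population, and name that population in 4.3.2.2 to 4.3.2.5. If a table of patients in both parts is wanted, label it as supplementary.

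State which part the Visit 5 or first extension day belongs to for TEAEs, and word the rule so that each event falls in exactly one part. One option is to count Part B events from the first day of Part B onward and end Part A the day before. Keeping that day in Part A, in line with the efficacy windows in 3.2, would also close the gap if stated.

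The cost is SAP wording and a changed denominator in the table programs. No new data are needed. Some overall rates may look less favourable, others more.
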